4.2.6 Follow-Up through End of Study

Study follow-up will continue via clinic visits through 40 weeks following the first vaccine administration. Refer to Section 4.4 which describes the criteria for discontinuing product administration and/or study participation.

4.2.7 Blood Sample Collection

At intervals throughout the study, blood will be drawn for safety and immunologic assays. Blood will be drawn from the arm veins of subjects by standard phlebotomy procedures. Total blood volume drawn from each subject will not exceed the NIH CC Guidelines.

4.2.8 Apheresis

Apheresis will be offered as an optional procedure at Visit 08 (except for Group 1). Each apheresis procedure will be carried out by trained Department of Transfusion Medicine (DTM) medical staff using automated cell separator devices.

All apheresis procedures performed under this protocol will be performed solely for research purposes. Prior to the scheduling apheresis, the subject must have a venous assessment performed by the DTM staff.

In order to undergo apheresis procedures, a subject must meet the apheresis eligibility criteria and have no medical contraindications, as determined by the DTM staff. A VRC study clinician will complete a checklist for apheresis eligibility before referring a subject for the procedure.

4.2.8.1 Apheresis Procedures

All study subjects will be treated according to standard whole blood and apheresis donation policies and procedures operative in the DTM.

For women of reproductive potential, a pregnancy test by blood or urine will be performed by a VRC study clinician within 72 hours prior to the apheresis procedure. Results must be negative to proceed with apheresis.

Prior to beginning the apheresis procedure, a study clinician may request in advance that other laboratory tests be collected as needed to monitor the well-being of the subject or samples as needed by a research laboratory.

The Dowling Apheresis Clinic staff at the NIH Clinical Center routinely performs a hemoglobin test prior to initiating apheresis, per DTM Apheresis Clinic standard policies. If a subject is found to have a hemoglobin value less than permitted by the Apheresis Clinic, then the apheresis will not be initiated and the ordering provider will be notified. The VRC Study Coordinator will provide the Apheresis center with a request for numbers and types of tubes of blood to be collected prior to beginning the apheresis.

In this study, the procedure will require two antecubital venous access sites and will involve processing 1 to 4 liters of whole blood. The expected mononuclear cell yield is approximately 0.5 to 1.0×10^9 cells per liter processed, and the apheresis device can process about 2-3 liters per hour. Thus, 1 to 2 hours are required to process 1 to 4 liters of blood and obtain about $1-4 \times 10^9$ leukocytes. The packed red cell loss during the procedure is the equivalent of a 6 mL blood draw; this is the volume that will be used for the purposes of calculating cumulative blood draw when apheresis is performed.

During or following an apheresis visit, if there is any concern about the well-being of the subject, the DTM clinic may conduct appropriate medical evaluations by history-taking, physical examination, laboratory tests, and/or other testing.

Research blood samples will be processed and stored at VITL or a collaborating research laboratory. Stored samples may be used later to further evaluate immune responses and to elucidate genetic factors associated with immune response.

4.2.9 Concomitant Medications

Only routine prescription medications will be entered in the database at the time of enrollment. Subsequently, concomitant medications associated with an AE requiring expedited reporting or the development of a new chronic condition requiring ongoing medical management will be recorded or updated in the database. Antiviral medications taken for influenza or influenza-like illnesses will be recorded in the database. Receipt of a FDA-approved vaccine at any time during the study will be recorded in the database (clinicians should work with subjects regarding the timing of licensed vaccines relative to study injection). Otherwise, concomitant medications taken throughout the study will be recorded in the subject's chart as needed for general medical documentation but will not be recorded in the database.

4.3 CRITERIA FOR DOSE ESCALATION AND DOSE CONTINUATION

There will be one dose escalation in this study. The Protocol Safety Review Team (PSRT, Section 8.8) will conduct an interim safety data review before dose escalation and repeat dosing

may occur. The PSRT must assess the data as showing no significant safety concerns before enrollment of the next dose level and repeat dosing at the same level may proceed.

Enrollment will begin in Group 1 (20 mcg of VRC-FLUNPF081-00-VP) with no more than one subject enrolled per day. Two weeks after vaccination of the fifth volunteer, there will be an internal safety review on all five subjects to determine whether to proceed to the next dose level. If the 20 mcg dose of VRC-FLUNPF081-00-VP vaccine is assessed as safe, enrollment will begin for Group 2.

In Group 2 (60 mcg of VRC-FLUNPF081-00-VP), enrollment continues with no more than one subject enrolled per day. Two weeks after vaccination of the fifth volunteer, there will be an internal safety review on all five subjects to determine whether to proceed to Part II. If the 60 mcg dose of VRC-FLUNPF081-00-VP vaccine is assessed as safe, subjects in Group 2 will proceed to receive a second vaccination at week 16 and enrollment can begin for all groups in Part II.

If a first vaccination is not completed or there are discontinuations from the study before there are sufficient data to conduct the dose escalation review for a group, then extra subjects may be enrolled into that group in order to have the requisite data on at least 5 subjects.

The IRB will be provided with documentation of the safety review process and notification of the dose escalation. Consultation with the IRB and FDA, if needed, as per study pause criteria (Section 4.5) will occur if indicated by the review. One outcome of a dose escalation review may be to recommend evaluation of additional subjects at the current dose level and reassess for safety before proceeding to a higher dose level and repeat dosing at the same dose level.

4.4 CRITERIA FOR DISCONTINUING STUDY INJECTIONS OR PROTOCOL PARTICIPATION

Decisions on discontinuation of study injections or protocol participation for a subject will be made by the site PI or designee.

4.4.1 Discontinuation of Study Injections

Subjects who receive at least one injection will continue follow-up according to the Schedule of Evaluations., except that the research sample collections will be discontinued for pregnant women or others in which it is contraindicated A subject may be discontinued from receiving study product for the following reasons:

1. Pregnancy.
2. Grade 3 AE assessed as related to study product (with the exception that self-limited Grade 3 solicited reactogenicity does not require discontinuation).
3. Grade 4 AE assessed as related to study product.
4. Immediate hypersensitivity reaction associated with study product.
5. Intercurrent illness that is not expected to resolve prior to the next scheduled study injection.
6. Treatment with systemic glucocorticoids (e.g., prednisone or other glucocorticoid) or other immunomodulators (other than nonsteroidal anti-inflammatory drugs [NSAIDs]), with the exception that study injections may continue per investigator discretion if the next dose occurs at least 2 weeks following completion of glucocorticoid treatment.

7. The study PI assesses that it is not in the best interest of the subject to continue on the vaccination schedule.

4.4.2 Discontinuation of Protocol Participation

A subject may be discontinued from protocol participation for the following reasons:

1. Subject decides to discontinue participation;
2. Subject develops a medical condition that is a contraindication to continuing study participation;
3. The IND sponsor or regulatory authority stops the protocol;
4. The PI assesses that it is not in the best interest of the subject to continue participation in the study or that the subject's compliance with the study is not sufficient.

4.5 CRITERIA FOR PAUSING AND RESUMING THE STUDY

4.5.1 Plan for Pausing the Study

The PI and Protocol Safety Review Team (PSRT) will closely monitor and analyze study data as they become available and will make determinations regarding the presence and severity of AEs. The administration of study injections and new enrollments will be paused and the IND Sponsor will be promptly notified according to the following criteria:

- **One** (or more) subject experiences a **SAE** assessed as related to study product.
- **Two** (or more) subjects experience the same **Grade 3 or higher unsolicited AE** assessed as related to study product.
- **Three** (or more) subjects experience the same **Grade 2 or higher laboratory abnormality** assessed as related to study product.

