4.2 CLINICAL PROCEDURES AND EVALUATIONS

Evaluation of this vaccine will include laboratory tests, medical history, physical assessment by clinicians, and subject self-assessment recorded on a diary card for 7 days after each injection. Potential adverse reactions will be further evaluated prior to continuing the vaccination schedule. The schedule of study evaluations is described in this section and shown in table format in Appendix II. Total blood volume drawn from each subject will not exceed the NIH CC Guidelines.

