Subjects will be given a “Diary Card” to use as a memory aid, on which to record temperature and symptoms daily for 7 days after each injection. Subjects will be trained and encouraged to use the secure electronic database but will have the option to complete a paper diary card. When the diary card parameters are recorded directly by the subject in the electronic database, the subject’s electronic record will be the source for these data. When collected on paper, the paper diary card will be used as a source document. When neither paper nor electronic diary is available from the subject, the study clinician will document the source of reactogenicity information recorded in the study database.

The solicited signs and symptoms on the diary card will include the following parameters: unusually tired/feeling unwell, muscles aches (other than at injection site), headache, chills, nausea, joint pain, and pain/tenderness at injection site. Subjects will also record the day’s highest measured temperature and measurement of largest diameter for redness and swelling at injection site.

Follow-up on subject well-being will be performed by telephone on the first day following all injections and by clinic visits as shown in the Schedule of Evaluations (Appendix II)

Events following any study injection that may require clinical evaluation include rash, urticaria, fever of 38.5°C (Grade 2) or higher lasting greater than 24 hours, or significant impairment in the activities of daily living. Additionally, other clinical concerns may prompt a study visit based on the judgment of a study clinician.

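### The Section 4.5.1 pause rule counts repeated related Grade 3 or higher events only if unsolicited, so non-serious Grade 4 solicited reactions and Grade 3 solicited reactions that are not self-limited have no numeric study-level trigger (minor)

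*Combined protocol and SAP*

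**What the plan says.** Section 4.5.1 pauses injections and enrollment on any of three counts:

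- one subject with a related SAE;
- two subjects with the same related "Grade 3 or higher unsolicited AE";
- three subjects with the same related laboratory abnormality of Grade 2 or higher.

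Section 4.4.1 works at subject level and is permissive: "A subject may be discontinued from receiving study product for the following reasons". Its list includes "Grade 3 AE assessed as related to study product (with the exception that self-limited Grade 3 solicited reactogenicity does not require discontinuation") and "Grade 4 AE assessed as related to study product". The Grade 4 item has no exemption for solicited events. Section 4.4 adds: "Decisions on discontinuation of study injections or protocol participation for a subject will be made by the site PI or designee".

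Other parts of the protocol also bear on severe solicited reactions:

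- **Section 4.2:** "Potential adverse reactions will be further evaluated prior to continuing the vaccination schedule".
- **Section 4.2.5:** events that may require clinical evaluation include Grade 2 or higher fever "lasting greater than 24 hours, or significant impairment in the activities of daily living".
- **Section 4.3:** "The PSRT must assess the data as showing no significant safety concerns before enrollment of the next dose level". The detailed steps are written for Groups 1 and 2.
- **Section 5.1:** solicited events come from a 7-day diary. Paper entries are transcribed without attribution, and attribution is provided for only with unsolicited AEs.
- **Section 8.8.1:** daily review by a safety officer, and weekly review by the Protocol Safety Review Team (PSRT) until 4 weeks after the last injection.

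**The concern.** The exclusion in 4.5.1 is wider than the exemption in 4.4.1. Section 4.4.1 sets aside only self-limited Grade 3 reactogenicity, whereas 4.5.1 sets aside every solicited reaction at every grade. A reaction that the protocol regards as a reason to stop one subject can therefore recur in a second subject, or a fifth, without meeting a pause criterion, provided it is not serious. No reason is given for the wider exclusion.

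Both vaccines are first-in-human. Once Group 2 has been reviewed, all Part II groups may open together. By plan, Groups 3A and 3B receive the first human doses of DNA A/Sing, and Groups 3B and 4B are the first subjects dosed at ages 52-70. That is 10 + 10 + 10 = 30 of 40 Part II subjects whose prime is a new exposure with no staged review before it. For these primes, 4.5.1 holds the only numeric study-level check. What is at stake is a prompt, mandatory pause with sponsor notification, as opposed to one that depends on judgment.

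**Working it through.** **Which solicited reactions escape the SAE trigger.** Section 4.2.5 lists 7 symptoms plus temperature, redness and swelling, so 10 parameters. Their Grade 4 definitions in Appendix III are:

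| Grade 4 defined by | Parameters | Number |
|---|---|---|
| Hospitalization (own row, or the general scale for chills and joint pain) | tiredness, muscle aches, headache, nausea, injection-site pain/tenderness, chills, joint pain | 7 |
| Necrosis (for redness, also exfoliative dermatitis) requiring medical attention | redness, swelling | 2 |
| Temperature above 40 C alone | fever | 1 |

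The first 7, if related, would in practice pause the study at one subject. The other 3 are serious only by judgment: Section 5.2 confines life-threatening to an immediate risk of death at occurrence, although 5.2 and 5.3 allow an important medical event to be called serious. Non-self-limited Grade 3 has no count for any of the 10 unless judged serious. Section 5.1 says that symptoms lasting beyond day 7 are followed to resolution, but not that they become unsolicited. As written, the probability that non-serious events of this kind meet a pause criterion is 0 at any true rate.

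**How often a two-subject count would be reached.** With X ~ Binomial(n, p),

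Pr(X ≥ 2) = 1 − (1 − p)^n − n p (1 − p)^(n−1).

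Table 6-1 gives this quantity as the probability of more than 1 event. Check at n = 10, p = 0.1: 1 − 0.3487 − 0.3874 = 0.264, as printed. All 36 cells of the table reproduce to rounding. At n = 10 (one Part II age cohort) the table gives 0.004, 0.086, 0.264 and 0.624 at p = 1%, 5%, 10% and 20%.

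The documents give no rates for these reactions, so the rates below are assumed and taken as equal in all groups. For one reaction type in the planned 50 subjects (Section 6.4):

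| True rate p | Pr(X ≥ 2), n = 50 |
|---|---|
| 0.1% | 0.001 |
| 0.5% | 0.026 |
| 1% | 0.089 |
| 5% | 0.721 |
| 10% | 0.966 |

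Example at 1%: 1 − 0.6050 − 0.3056 = 0.0894.

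**Cost over all ten parameters.** If q is the value above and the 10 parameters were independent at the same rate, 1 − (1 − q)^10 gives 0.012, 0.233 and 0.608 at p = 0.1%, 0.5% and 1%. Independence is a rough assumption, because fever, chills, aches and headache tend to occur together. In the 1% case, 1 − 0.99^10 = 0.096, so about one subject in ten would have some such reaction, which would merit review in any case.

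**The case against.** The strongest reply is that 4.4.1 and 4.5.1 serve different purposes and need not match: one is permissive and concerns one subject, the other is mandatory and stops the study. Leaving self-limited Grade 3 reactogenicity out of the pause rule looks deliberate and is reasonable.

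The protocol also has safeguards beyond those quoted. Under Section 5.4 an unanticipated problem, serious or not, goes to the IRB within 7 calendar days, and expected AEs above the rate known in healthy adults are handled in the same way. Section 8.5 describes expected general reactions as mostly mild to moderate, so a related fever above 40 C could plausibly qualify. An investigator or sponsor may call such an event serious, and one related SAE pauses the study. Section 9.1 gives several bodies power to terminate. The opening of Section 4.3 refers to PSRT review before repeat dosing in general terms and could be read to cover Part II boosts, though not Part II primes. More than 3,000 people have received other VRC DNA vaccines (Section 1.3.1), so expected risk is low.

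All of this stands and limits the weight of the point. None of it supplies a count.

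A reader might infer that severe solicited reactions go unmonitored, or that Grade 4 solicited reactions generally cannot pause the study. The safeguards above and the 7 hospitalization-defined parameters rule out both readings. A reader might also infer that 5.1 contradicts 4.4.1, since relatedness cannot be applied to events recorded without attribution. Appendix III lets the investigator assess any AE, so 4.4.1 can be applied. What is missing is a stated place to record that judgment for a solicited event.

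**Conclusion.** The gap holds on the text, and it is minor. Non-serious Grade 4 solicited reactions, and Grade 3 solicited reactions outside the self-limited exemption, have no numeric study-level pause trigger, although 4.4.1 lists both, when related, as grounds to stop a subject's injections. The remaining safeguards rest on judgment or reporting.

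No endpoint estimate is affected, because Section 6.5.3.1 tabulates reactogenicity by severity without attribution. The probabilities rest on assumed rates. They show that a two-subject count is seldom reached for rare events and usually reached at 5% or more across 50 subjects. They do not show that such rates are likely, and for fever above 40 C the documents give no support for rates of 5% or higher.

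**What to change.** Extend the second criterion of Section 4.5.1 so that it is met by two or more subjects with any of the following, judged related to the study product:

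- the same "Grade 3 or higher unsolicited AE" (unchanged);
- the same Grade 4 solicited reaction;
- the same Grade 3 solicited reaction that led to discontinuation of injections under 4.4.1.

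In Section 5.1, have the clinician record attribution for these few solicited events, whether the diary is paper or electronic. Keep self-limited Grade 3 reactogenicity exempt.

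Tying the Grade 3 limb to an actual discontinuation avoids having to define self-limited by duration or treatment. A day-7 cut-off would be arbitrary. A treatment-based test would misfire, because the Appendix III Grade 3 wording already names a treatment or intervention for nausea, chills, joint pain, injection-site pain and headache.

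One limit follows: the Grade 3 limb can act only after a prime in the two-injection groups (50 − 5 = 45 planned subjects), since nothing is left to discontinue after a last injection. The Grade 4 limb applies after every injection.

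The cost is two clauses in 4.5.1, one sentence in 5.1, slight extra data entry, and a rare pause review that briefly delays injections and enrollment.

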4.5.2 Plan for Review of Pauses and Resuming the Study

The IND Sponsor, with participation by the PI and PSRT, will conduct the review and make the decision to resume, amend or close the study. As part of the pause review, the reviewers will also advise on whether the study needs to be paused again for any subsequent AEs of the same type. The pause criterion for the SAE will continue to apply.

The administration of study injections and new enrollments would resume only if review of the AEs that caused the pause resulted in a recommendation to permit further study injections and enrollments. Safety data reports and changes in study status will be submitted to relevant regulatory authorities in accordance with Section 5 and institutional policy.

5. SAFETY AND ADVERSE EVENT REPORTING

5.1 ADVERSE EVENTS

An adverse event (AE) is any untoward or unfavorable medical occurrence in a human subject, including any abnormal sign (e.g., abnormal physical exam or laboratory finding), symptom, or disease temporally associated with the use of study treatment, whether or not considered related to the study treatment.

Each AE will be graded according to the Table for Grading Severity of Adverse Events (Appendix III). The following guidelines will be used to determine whether or not an AE is recorded in the study database:

- Solicited AEs (i.e., reactogenicity parameters) will be recorded by the subject in paper or electronic diary cards for 7 days after each injection. If paper diary card is completed by subject, data will be transcribed by clinician into the study database without attribution assessments. Clinicians will follow and collect resolution information for any reactogenicity symptoms that are not resolved within 7 days.
- All unsolicited AEs will be recorded in the study database from receipt of first study injection through the “Week 4” visit after each study injection with attribution assessments. At other time periods between injections and when greater than 4 weeks after the booster injection, only SAEs (Section 5.2), new chronic medical conditions, and influenza or influenza-like illness (ILI) will be recorded through the last study visit.
- Cases of influenza or influenza-like illness will be evaluated using clinical judgment and current CDC definition of influenza symptoms (<https://www.cdc.gov/flu/about/disease/complications.htm>) and recorded on a case report form rather than on an AE form. ILI is defined as fever (temperature of 100F [37.8C] or greater) and a cough and/or sore throat in the absence of a known cause other than influenza.

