6.3 ENDPOINTS

6.3.1 Primary Endpoints: Safety

Assessment of product safety will include clinical observation and monitoring of hematological and chemical parameters. Reactogenicity will be closely monitored for 7 days after each injection and safety evaluated by clinical visits throughout 40 weeks. See Section 4.2 and Appendix II for details and specified time points.

The following parameters will be assessed for all study groups:

- Occurrence of solicited local reactogenicity symptoms for 7 days following each injection
- Occurrence of solicited systemic reactogenicity symptoms for 7 days following each injection
- Change from baseline in safety laboratory measures
- Occurrence of AEs of all severities through the “Week 4” visit after each injection
- Occurrence at any time throughout the study of SAEs or new chronic medical conditions that require ongoing medical management.

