6.5.6 Interim Analyses

Safety Reviews: The PSRT will review safety data routinely throughout the study. The study will utilize both electronic database features and reviews by designated safety review personnel to identify in a timely manner if any of the safety pause rules of the study are met.

Immunogenicity Review: The analyses of immunogenicity may be performed when the HAI assays of samples are collected at 4 weeks after the prime vaccination and at 2 weeks after the boost vaccine. This may occur prior to completion of safety follow-up visits or collection of data for secondary and exploratory immunogenicity endpoints. Such an analysis would constitute the final analysis for the primary immunogenicity endpoint, so sample size adjustments are not required. Reports providing results by study group may be provided to VRC solely for the purpose of informing decisions related to future trials in a timely manner. The results should in no way influence the conduct of the VRC 316 trial in terms of early termination or later safety or immunogenicity endpoint assessments. Analyses of secondary and exploratory immunogenicity assays may also be performed as data become available.

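### The two-subject Grade 3+ pause rule has no defined database source for non-serious clinical events starting between the Week 4 visit and the boost

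*Combined protocol and SAP*

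**What the plan says.** **Recording (5.1).** The section first says that every AE is graded. It then introduces its windows with "The following guidelines will be used to determine whether or not an AE is recorded in the study database", so the windows govern database entry. Within them, "All unsolicited AEs will be recorded in the study database from receipt of first study injection through the “Week 4” visit after each study injection"; each such entry carries a judgement of relatedness. Outside them the rule is narrower: "At other time periods between injections and when greater than 4 weeks after the booster injection, only SAEs (Section 5.2), new chronic medical conditions" go into the database, the one further category being influenza or ILI.

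**Endpoint (6.3.1).** The primary AE endpoint uses the same window: "Occurrence of AEs of all severities through the “Week 4” visit after each injection".

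**Pause rules (4.5.1).** "The administration of study injections and new enrollments will be paused and the IND Sponsor will be promptly notified according to the following criteria": one related SAE; a matching related unsolicited AE of Grade 3 or above in two or more subjects; or a matching related laboratory abnormality of Grade 2 or above in three or more. None of the three carries a time limit.

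**Individual rule (4.4.1).** Related Grade 3 AEs (self-limited solicited reactogenicity excepted) and related Grade 4 AEs are among the reasons a subject may be taken off injections. No time limit is stated. Section 4.4 gives the decision to the site PI or designee.

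**How pause triggers are found (6.5.6).** "The study will utilize both electronic database features and reviews by designated safety review personnel to identify in a timely manner" whether a pause rule has been met. Section 8.8.1 adds a daily Safety Officer review of clinical data and PSRT review of summary safety reports, weekly until 4 weeks after the last injection.

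**The concern.** The second pause rule counts across subjects and needs two inputs for each event: that it occurred at Grade 3 or above, and that it was judged related. Section 5.1 puts both in the database only up to the Week 4 visit. A delayed skin or joint reaction at Week 8 that prevents daily activity and needs treatment meets the generic Grade 3 definition in Appendix III. It need not be serious or chronic. If it is neither, 5.1 provides no database entry for it.

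The stake is the second injection. Both products are first-in-human. Section 4.3 sets a formal review two weeks after the fifth Group 2 subject's first injection, but names no separate pre-boost review for Groups 3 and 4. For those 40 subjects, the pause rules and the routine PSRT review are the cross-subject check before the boost. If two of them had the same late reaction, the plan gives no defined route by which the first case would be on file when the second appeared.

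The point concerns symptoms and diagnoses. It does not concern the scheduled laboratory panels or influenza illness.

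**Working it through.** The plan states no figure for this gap, so there is none to reproduce.

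**Inputs.** Week 4 visit (Visit 05): Day 28, ±2 days. Boost (Visit 06): Day 112, ±28 days. Last visit: Day 280 (all Appendix II). Targets: Group 2, 5; Group 3, 20; Group 4, 20 (Table 2), so 5 + 20 + 20 = 45.

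**1. Length of the gap.** Share = (boost day − Week 4 visit day) / boost day.
- Nominal: (112 − 28)/112 = 84/112 = 75.0%.
- Earliest boost, latest Week 4 visit: (84 − 30)/84 = 54/84 = 64.3%.
- Latest boost, earliest Week 4 visit: (140 − 26)/140 = 114/140 = 81.4%.

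Appendix II shows no scheduled visit for Groups 2 to 4 between Day 28 and Day 112. Over the whole study, full recording covers (28 + 28)/280 = 20% of days in Groups 2 to 4. Group 1 has no boost, so the pre-boost share does not apply to it.

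**2. Which events fall in the gap.**

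| Related clinical event, onset after the Week 4 visit and before the boost | Entered under 5.1? | Pause rule supplied with data? |
|---|---|---|
| SAE | Yes | Yes, one case suffices |
| Grade 4 (generic definition: hospitalization or intervention to prevent death) | Mostly, as an SAE | Mostly |
| New chronic condition; influenza or ILI | Yes | Entry exists |
| Other non-serious Grade 3 event | No | No defined database source |

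Only the last row is affected.

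**3. What the gap could do to the count (illustration with assumed rates).** P(at least 2 of n) = 1 − (1 − p)^n − np(1 − p)^(n−1).
- Suppose a share p of the 45 had the same related, non-serious Grade 3 event within the gap. The chance of reaching two cases is 0.227 at p = 2%, 0.665 at 5% and 0.948 at 10%. Under 5.1 none of these cases would be entered.
- Timing matters more. Take n = 40 and a 10% risk over the 16 weeks. With full recording the chance of two recorded cases is 0.92.
- With constant hazard and recording only through Week 4, p = 1 − 0.90^(1/4) = 0.026 and the chance falls to 0.28.
- If 80% to 90% of events began by Week 4 (p = 0.08 to 0.09), it is 0.84 to 0.89.

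Constant hazard is a pessimistic case, because vaccine reactions would be expected to cluster early. The documents give no rate or onset distribution for late reactions, so these figures show sensitivity only.

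**The case against.** The strongest reply is that 5.1 limits data entry, not clinical knowledge. Each AE is graded without a stated window, and Appendix III has the investigator assess relationship without one. Section 4.5.1 is triggered by what subjects experience, as determined by the PI and PSRT, and 6.5.6 names reviewers as well as the database. This is a single site with about 50 subjects, whose study clinicians sit on the PSRT. The Week 4 window matches the primary endpoint and looks deliberate.

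Much of that stands, and it rules out several stronger readings.
- A reader might infer that the stopping and pause rules are blind for 75% of the pre-boost period. They are not. SAEs are recorded throughout and reported within 24 hours, and most Grade 4 clinical events would be SAEs.
- A reader might infer that late Grade 3 events are neither graded nor attributed. The documents restrict only database entry.
- A reader might infer that the individual rule in 4.4.1 fails too. It is a permissive PI decision. Section 4.2 requires potential reactions to be evaluated before the schedule continues, 4.2.4 requires clinical evaluation before each injection, and Appendix II has interim history at Visit 06.
- A reader might infer that two identical late events could not trigger a pause. Reviewers may know of both; the plan does not make sure of it.

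What the reply does not supply is a defined route from chart to count. Evaluation before injection protects the subject in the room; the pause rule compares subjects. Under 4.2.9 most concomitant medication also stays in the chart, so treatment of such an event would usually leave no database trace.

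**Conclusion.** The concern holds in narrow form. In Groups 2 to 4, a related Grade 3 clinical event that is non-serious, non-chronic and not ILI, starting between the Week 4 visit and the boost, has no defined database source for the two-subject pause rule. The period is nominally 84 of 112 pre-boost days, or 64% to 81% across visit windows. That measures time, not the proportion of events missed. If reactions cluster early, the loss of detection is small.

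The conclusion rests on reading the absence of a time limit in 4.5.1 as meaning that the rule runs throughout. If the sponsor intends it to operate only within the recording windows, the text should say so. The documents do not settle which was meant.

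**What to change.** In 5.1, add unsolicited AEs of Grade 3 or higher, with attribution, to the events recorded outside the Week 4 windows through the last visit. In the AE tables or listings, show those with onset after Week 4 separately. Leave the Week 4 definition of the primary AE endpoint in 6.3.1 unchanged.

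The sponsor should also reconcile 4.4.1, 4.5.1 and 5.1, so that the period the rules cover and the data recorded for them agree. Which events count toward stopping or pausing is the sponsor's decision.

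The cost is one phrase in 5.1, a few more AE forms and a small chance of an additional pause review. Interim history is already taken at Weeks 16, 28 and 40, so no visit is added. For the same reason, the change will not usually bring earlier detection within a subject. Its value is that a case learned of at one subject's boost visit is on file when the next subject is considered.
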